Official Title: Development and Preliminary Examination of Two Brief Personalized Feedback Interventions Focused on Lab-based and EMA Alcohol Cues to Reduce Hazardous Young Adult Alcohol Use

Brief Title: Testing Brief Personalized Feedback Integrating Lab-based Alcohol Cue Information (Project ACE)

NCT number: NCT05873556

Document date: February 15, 2025

STATISTICAL ANALYSES

Prior to any inferential statistics, univariate and bivariate descriptive statistics will be used to assess distributions for baseline data and 2-week and 3-month follow-up data. Given the repeated measures design, generalized linear mixed models (GLMM; Raudenbush & Bryk, 2002) will be used. GLMM (aka hierarchical generalized linear models) allow for non-normal outcomes and missing data, handle varying time-points, and accommodate time-varying and time-invariant covariates. Separate models will test for intervention effects on craving, alcohol use, and consequences. Hypotheses compare the Cue Reactivity PFI to the assessment-only control (AOC). Models include three repeated measures (baseline, 2-week, 3-month) where Level 1 refers to repeated-measures and Level 2 refers to people. To determine whether the EMA-based PFI is associated with reduced drinking and negative consequences at the follow-ups, we will use Poisson forms of regression models, which are appropriate for count outcomes. The following equations represent the basic analytic model and serve as the basis to test intervention effects with drinking as an example:

```
Level 1: \log(\text{E}[\text{Alcohol}_{ti}]) = \pi_{0i} + \pi_{1i}(\text{Time1})_i + \pi_{2i}(\text{Time2})_i + \varepsilon_{ti} \varepsilon_{ti} \sim N(0, I\sigma_{\varepsilon}^2)

Level 2: \pi_{0i} = \beta_{00} + \beta_{01}(\text{Intervention Condition})_i + r_{00i}

\pi_{1i} = \beta_{10} + \beta_{11}(\text{Intervention Condition})_i + r_{10i}

\pi_{2i} = \beta_{20} + \beta_{21}(\text{Intervention Condition})_i + r_{20i}
```

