where t indexes repeated-measures and i indexes participants. $Alcohol_{ii}$ represents the outcome measured at each time point for each individual. Time will be coded as two dummy variables that compare the 2-week (Time1) and 3-month (Time2) follow-ups to baseline (reference category). Intervention Condition will be a dummy variable to compare the PFI condition to the AOC condition (reference). Of particular interest are parameters that reflect the interaction between intervention condition and Time (e.g., β_{21} at 3-month). For count outcomes, the outcome is connected to covariates through a log link function, which is the standard link function for Poisson GLMM. Covariates can be exponentiated to yield Rate Ratios (RRs) that describe the proportional change in the count outcome associated with a 1-unit increase in the covariate. If data show over-dispersion where the variance exceeds the mean, the model will be extended to include a scale parameter to fit an over-dispersed Poisson, or we will consider zero-altered models to ensure accurate inferences (Atkins et al., 2013; Atkins & Gallop, 2007). We will also consider adding baseline covariates to improve precision or if evidence suggests an imbalance in the distribution of the covariate(s) across conditions.

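### Does leaving open a scaled Poisson or a zero-altered model for over-dispersed counts leave the intervention effect undefined?

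*SAP*

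**What the plan says.** All of this is in the SAP, Statistical Analyses.

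- Before any inference, "univariate and bivariate descriptive statistics will be used to assess distributions for baseline data and 2-week and 3-month follow-up data". Nothing is said about whether this is done by condition or blind to it.
- For drinking and consequences, "we will use Poisson forms of regression models, which are appropriate for count outcomes". The two-level equations are introduced thus: "The following equations represent the basic analytic model and serve as the basis to test intervention effects with drinking as an example". They contain person-level random effects and a log-scale Level 1 residual.
- The target is named after the equations: "Of particular interest are parameters that reflect the interaction between intervention condition and Time". β_21 at 3 months is the example, and effects are exponentiated to rate ratios.
- The fallback has one trigger, "If data show over-dispersion where the variance exceeds the mean", and two responses: "the model will be extended to include a scale parameter to fit an over-dispersed Poisson, or we will consider zero-altered models".

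Neither document gives a sample size, alpha, expected effect, mean count or proportion of zeros.

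**The concern.** One trigger leads to two models, no rule chooses between them, and the follow-up distributions are inspected first. Adding a scale parameter alters the standard errors but not the target. A zero-altered model replaces each condition-by-time ratio with two parameters. In a hurdle model the count part compares only participants who drank, and the intervention can change who those are, so taken alone it is not a comparison of the randomised groups. If the PFI moves light drinkers to zero, the remaining drinkers average more, and the count part could suggest no benefit or even harm while total drinking fell. If success could be claimed on either part, the false-positive rate would rise. A trigger judged on raw counts might also fire very easily.

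**Working it through.** The plan has no figure of its own to reproduce. Every numerical input below is an assumption.

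**1. When the targets differ.** For a two-part model, overall mean = (1 − p0) × mean among drinkers, where p0 is the proportion of zeros. Hence overall ratio = [(1 − p0,PFI)/(1 − p0,AOC)] × ratio among drinkers.

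- Equal zeros in both arms: the two ratios coincide.
- Zeros 20% (AOC) against 40% (PFI), same mean among drinkers: overall 0.60/0.80 × 1.00 = 0.75, against 1.00 among drinkers.

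So the options can diverge.

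**2. Size in plausible cases.** Take a negative binomial control arm with mean 4.5 and k = 0.685. This gives 25% zeros, 14.9% with exactly one drink, and drinkers averaging 6. Move a share f of participants from one drink to none and multiply the remaining drinkers' counts by c:

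- overall = c(4.5 − f)/4.5
- among drinkers = c[(4.5 − f)/(0.75 − f)]/6
- odds ratio for zero = [(0.25 + f)/(0.75 − f)]/(0.25/0.75)

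| Case | Overall | Among drinkers | OR for zero |
|---|---|---|---|
| f = 0.05, c = 1 | 0.99 | 1.06 | 1.29 |
| f = 0.10, c = 1 | 0.98 | 1.13 | 1.62 |
| f = 0.10, c = 0.9 | 0.88 | 1.02 | 1.62 |
| Uniform 20% cut (mean 3.6, same k) | 0.80 | 0.84 | 1.19 |

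Under a general reduction the gap is small. In the two pure-shift rows the overall fall is 1-2%, too small to detect. The third row is the one that counts. It needs 0.10/0.149, about two-thirds, of one-drink participants to stop and everyone else to cut by 10%.

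**3. Could the all-participant analysis detect 0.88?** Simulated power for a 30% fall, with 100 per arm, was 33.3% to 48.9%. Keep that standard error on the log scale.

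- Power 33.3%: 1.96 − 0.43 = 1.53 standard errors, so SE = 0.357/1.53 = 0.233. For 0.88, 0.128/0.233 = 0.55 standard errors, giving about 8% power.
- Power 48.9%: 1.96 − 0.03 = 1.93, so SE = 0.357/1.93 = 0.185. For 0.88, 0.128/0.185 = 0.69, giving about 11%.

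Fixing the all-participant ratio would rarely rescue this case.

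**4. False positives.** If either part could be claimed at 0.05 and the two were independent, the rate at one follow-up would be 1 − 0.95² = 0.0975. Simulation (50-100 per arm, zeros 11-29%) gave 8-11%, against 4-6% for either part named in advance. This measures a two-part claim, which the SAP does not make. It is not the error from choosing between the two models.

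**5. The trigger.** For a Poisson model with a log-normal person intercept, raw variance/mean = 1 + μ(exp(SD²) − 1). At μ = 4 and SD 0.3, 0.5 or 0.8 this is 1.4, 2.1 or 4.6, so a raw-count reading would fire even when the basic model is right. But the SAP speaks of extending the model, which can equally mean dispersion beyond what the fitted model explains. The Level 1 residual already allows some extra-Poisson variation.

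**6. Would one fixed count model be better?**

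- Zeros 35% against 20% at follow-up, equal counts among drinkers, 100 per arm: power for the condition-by-time contrast is 16% for the all-participant ratio and 48% for the zero part.
- A general 30% fall reverses the order: 33-49% all-participant, 12-16% zero part, 23-33% count part.
- Keeping log-normal person effects, as the SAP's equations do, can miss the all-participant ratio when participants move to zero. A single-wave log-normal Poisson fit with common SD gives exp(β) = 0.913 against a true 0.978 at f = 0.10, and 0.958 against 0.989 at f = 0.05. A negative binomial without person effects gives 0.978 at f = 0.10.

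**The case for a change.** The strongest case for a change is that a lean is not a rule. The SAP is firm about the scale parameter and only tentative about zero-altered models, yet it gives no zero-proportion criterion or fit statistic, and the analyst will have seen the outcome data. Reducing drinking is the purpose of the intervention, so a shift to zero is a plausible effect. A preliminary trial still needs an interpretable result, and a sentence or two would settle the matter.

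Part of this stands. The SAP does not say which component of a zero-altered model answers the hypothesis, or when that model is used. It does not follow that no effect is fixed in advance: the condition-by-time rate ratio is named, and the scaled Poisson retains it. The misleading reading also requires the count part to be shown without the zero part, although in the motivating scenario the zero part displays the shift (odds ratio 1.62).

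**Conclusion.** No change is needed. The gap is real but narrow: an optional fallback has no selection rule and no named component. An analyst who used a zero-altered model would ordinarily report both parts, and the two together give the all-participant ratio through the identity in step 1. Describing distributions before modelling is normal practice, and the SAP does not say that it is done by arm.

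The size is modest. The ratios separate materially only when the intervention changes the proportion of zeros, and the case most often feared (0.88 against 1.02) would have about 8-11% power in the all-participant analysis with 100 per arm. Committing to one count model would not be a clear gain. It gives up power if the effect runs through abstinence (16% against 48%), and with log-normal person effects its coefficient need not equal the all-participant ratio. For a trial whose title calls it preliminary, leaving this choice open is a fair trade-off.

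This rests on assumed zero proportions, means and arm sizes, and on simulated contrasts of cell means rather than the fitted mixed model. The conclusion would differ if the SAP allowed success to be claimed on either part, or planned to report the count part alone. It does neither.
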